## **A. SPECIFIC AIMS**

Populations all over the world are experiencing rapid increases in the prevalence of obesity and diabetes [1-5]. To date, the public health response to the emerging obesity epidemic has been almost totally ineffective. As a first line of response, professional bodies and government organizations have issued prevention guidelines, all of which include recommendations on levels of activity energy expenditure (AEE) [6-10]. However, even if fully implemented, it is not clear that the current recommendations on AEE would impact the trend in age-related weight gain. *In fact, there is virtually no direct evidence that can be brought to bear on the question of whether the obesity epidemic has resulted primarily or even partially from society-wide declines in habitual physical activity (PA).*

To date, epidemiologic research on AEE has relied on very crude measurement tools—primarily questionnaires. These self-reported data capture only a small fraction of the total variance in activity and are potentially confounded when they focus on leisure-time PA. By contrast, direct measurement with doubly labeled water (DLW) provides a precise, unbiased estimate of all forms of non-resting energy expenditure. DLW has also been used to validate the new generation of accelerometers which are efficient measurement tools for larger studies.

In this application we request support to apply these objective measurement tools to examine the “ecology of AEE”. The study will take place in 5 countries, spanning the range of the activity-obesity spectrum, and combine both within-population person-level and between-population ecological analyses. First, we will examine whether an individual’s amount or pattern of AEE is related to adiposity in a diverse sample of 2,500 (i.e., 500 subjects/site x 5 sites). Second, we will test the ecological hypothesis that a decline in levels of AEE is an important cause of the rapid increases in obesity that are currently taking place in many societies. As an exploratory aim we will examine the role of selected adipocytokines and the appetite hormone ghrelin.

*Accordingly, we propose to test the following Hypotheses:*

- 1) AEE is negatively related to percent body fat in the 5 study populations at baseline, independent of dietary intake.
- 2) AEE is negatively related to change in body weight during follow-up, independent of dietary intake.

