**Figure 1. BMI Trend in US Population**

obesity expert: “Clearly some kind of change in energy balance has occurred, but we have surprisingly little ability to explain exactly why this has happened. Why was BMI relatively stable and why did it begin to increase fairly suddenly? Despite the intense attention paid to obesity and numerous hypotheses that have been put forward, we still lack explanations supported by data, and we lack understanding of the mechanisms driving these changes” [28]. The central purpose of our proposed project is to test whether change in AEE can be identified as a contributory mechanism to the population-wide weight gain, and, if so, to quantify its importance.

[figure not shown]

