We acknowledge that the energy balance models presented here are simplified to allow valid hypothesis testing. We submit, however, that the basic model is no different from established risk factor mechanisms. Thus, a diet high in saturated fat and cholesterol leads to a gradual increase in serum LDL over a lifetime, independent of other modifying factors and without the assumption that diet composition continues to change over time. The same logic applies to the impact of a high salt diet on blood pressure. In our framework low AEE is therefore being characterized as a classic chronic disease lifestyle risk factor. **AEE should be detectable as a risk factor when measured with precision in an adequately powered sample.**

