#### D.7.1.3 Comparison of Mean AEE Levels Among Sites

The 2 sample t-test will be used to compare means of the primary continuous variables, e.g., BMI, PA, weight, and height. Relevant co-variates will be identified from the within-site analyses and added using multivariable models [186, 190]. We recognize that some modifying factors within sites may not have the same significance across sites, and we will be very careful how variables are chosen for these analyses. Finally, we will test whether the regression slopes of the PA-BMI relationship varies significantly among any pair of sites (i.e., test for interaction).

The association between mean levels of AEE and mean levels of obesity/relative weight will be assessed using regression analysis, following a meta-regression type of approach. That is, mean AEE values will be regressed on mean obesity/relative weight values, weighting by the inverse of the squared standard error of the mean AEE values [191]. This is a widely-used approach in meta-analysis [192]. It is recognized that EI is an important potential confounder of the associations at the individual level. We will estimate the median (and other quantiles of the distribution) usual intake of nutrients (e.g. fat, percent fat) using methods developed by the ISU research group [179, 193] and include them in the meta-regression models.

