Although the study is not powered to test for differences in the association across sites (i.e., effect modification), we will undertake this task to ensure that large differences among the correlation coefficients do not exist. In addition, sites in which the correlation coefficient is deemed to be similar will be combined, and then comparisons of the correlations will be performed. For the sake of illustration, assume that 2 sites ( $n = 150$  individuals) are compared to other 2 sites ( $n = 150$  individuals). Thus, a two-sample, one-sided test of the correlations, assuming -0.4 versus -0.65, will yield over 91% power, whereas the power will be over 80% for comparison of -0.45 and -0.65, and between -0.35 and -0.6 the power is greater than 85%. Combining the data samples from all 5 sites and assuming constant

association will demonstrate a correlation between AEE and change in body composition of -0.15 or smaller (larger in absolute value) with over 83% power.

3) Mean levels of AEE are negatively related to mean levels of obesity/relative weight among the populations.

As previously demonstrated, sample sizes within sites will allow us to rule out correlations larger than 0.33 (absolute value), even when AEE is determined by DLW. Furthermore, we have estimated (cf. Preliminary Studies) that the within-site correlation between AEE and body composition of individual data could be as large as 0.6. We anticipate that the correlation between mean AEE levels and mean body composition will exceed 0.85. This estimate is justified in the following manner. A Fisher's Z-transformation 5%-significance test will have over 55% power to detect this correlation with 5 values corresponding to the 5 sites of the study. However, after dividing our samples by gender there will be 10 observations (2 X 5 countries), resulting in over 95% statistical power. Assuming an effective sample size of 7, to account for within-country correlations, the statistical power is 80%. Note that additional power will be gained when weighted linear regression methods are applied to estimate the correlation (slope) between AEE and body composition using meta-regression. Given the strong a prior hypothesis we can also compare mean AEE in the groups with the highest and lowest rates of obesity to test the ecological association.

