## **HUMAN SUBJECTS**

### **E.1 Risks to the Subjects**

This study will involve the collection of medical information, activity data, plasma and urine samples from 2,500 human participants, ages 25-45 years, from communities in 5 countries. The participants will be recruited from residential neighborhoods in Igbo-Ora, Nigeria; Cape Town, South Africa; Seychelles; Spanish Town, Jamaica; and Maywood, IL, USA. Participants will be recruited for this study as the primary aim is to determine whether or not differences in energy expenditure are responsible for the differences in relative weight, change in relative weight over time, and diabetes risk between these countries.

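### The Hypothesis 3 meta-regression makes mean AEE the dependent variable and weights by its precision, so its slope is not the obesity difference per unit of AEE that the study asks about

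*Combined protocol and SAP*

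**What the plan says.** Section D.7.1.3 describes the population-level analysis for Hypothesis 3: "mean AEE values will be regressed on mean obesity/relative weight values, weighting by the inverse". The weights are specified in the same sentence: "weighting by the inverse of the squared standard error of the mean AEE values". Quantiles of usual nutrient intake are then added to these models because energy intake is a recognised confounder.

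Other sections give AEE the opposite role:

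- A. Specific Aims: "we will test the ecological hypothesis that a decline in levels of AEE is an important cause of the rapid increases in obesity".
- B.6: "low AEE is therefore being characterized as a classic chronic disease lifestyle risk factor".
- E.1: "the primary aim is to determine whether or not differences in energy expenditure are responsible for the differences in relative weight".
- Table 5 lists the accelerometer as an exposure, and body composition and anthropometrics as outcomes.
- D.7.1.2 models weight change with AEE as the predictor, both in the simple regression and in the multilevel model.

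The text beside Figure 1 says the central purpose is to find out whether change in AEE contributes to population weight gain and, "if so, to quantify its importance".

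Hypothesis 3 itself is worded symmetrically, as a negative relation between two sets of means. D.7.2, item 3, plans it through a correlation expected to exceed 0.85 in size. It then says power will be gained when "weighted linear regression methods are applied to estimate the correlation (slope) between AEE and body composition using meta-regression", without naming the dependent variable.

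**The concern.** A regression slope has a direction even when the hypothesis does not. In the usual sense of regressing one variable on another, D.7.1.3 puts mean AEE on the left-hand side. The weights support that reading, because inverse-variance weights in a meta-regression come from the precision of the dependent variable. The sentence is therefore consistent within itself and cannot be dismissed as loose word order, but it runs against the rest of the protocol.

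Three things are at stake:

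- **The estimate.** The coefficient would be in kcal/d per BMI unit (or per unit of another obesity measure). Quantifying the importance of AEE needs obesity per unit of AEE.
- **Comparison between levels.** B.7 relies on consistency between person-level and population-level findings, and D.7.2 guards against ecological confounding by looking at individual-level relationships first. The person-level slopes have AEE as predictor, so a population-level slope with AEE as outcome cannot be placed beside them.
- **The weights.** Each group mean would count according to how precisely AEE is measured there, when the model that answers the question needs the precision of mean obesity.

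**Working it through.** **Inputs.** Regression direction and weights: D.7.1.3. Planned |r| = 0.85, 5% test, and 5, 10 or an effective 7 points: D.7.2, item 3. Within-group standard deviations of AEE (kcal/d) and of population BMI: Table 1. Equal numbers of men and women per site: D.3.2.

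**1. The plan's own power figures.** Power = Φ(√(n − 3) · atanh(0.85) − z), with atanh(0.85) = 1.256 and one-sided 5% z = 1.645.

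| n | √(n − 3) · 1.256 − 1.645 | Power | Plan states |
|---|---|---|---|
| 5 | 0.132 | 55.2% | over 55% |
| 7 | 0.867 | 80.7% | 80% |
| 10 | 1.679 | 95.3% | over 95% |

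The figures are reproduced with a one-sided test. Two-sided they would be 42.7%, 71.0% and 91.4%. The calculation uses only r and n, so it does not depend on which variable is the outcome.

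**2. What the written model estimates.** Let s_A and s_B be the standard deviations of the AEE means and the obesity means.

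- Slope as written (AEE on obesity): r · s_A / s_B, in kcal/d per unit of obesity.
- Slope the question needs (obesity on AEE): r · s_B / s_A, in units of obesity per kcal/d.
- Inverse of the written slope: s_B / (r · s_A), which equals the needed slope divided by r².

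So the needed slope is not the reciprocal of the written one. The ratio of inverted to direct slope is 1/r²:

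- |r| = 0.85: 1/0.7225 = 1.38
- |r| = 0.90: 1/0.81 = 1.23
- |r| = 0.95: 1/0.9025 = 1.11

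With one common set of weights the identity is exact, with the weighted r in place of r. With intake covariates, the partial r takes its place.

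**3. The zero-slope test.** In either direction t = r√(n − 2) / √(1 − r²). At n = 7 and r = −0.85, t = −0.85 × 2.236 / 0.527 = −3.61 both ways. In 20,000 simulated data sets at each of n = 5 and n = 10, with unequal but common weights, the two t-statistics never differed by more than 1e-10. The same symmetry holds for the partial t when both models carry the same covariates.

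**4. The weights.** With equal numbers per sex-by-site group (an assumption, following the equal-sex recruitment in D.3.2), each group's share of the weight is (1/SD²) / Σ(1/SD²) over the ten groups.

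| Group | SD of AEE | Share, AEE weights | SD of population BMI | Share, BMI weights |
|---|---|---|---|---|
| Nigerian women | 230 | 17.8% | 6.0 | 8.8% |
| Jamaican men | 306 | 10.1% | 4.5 | 15.6% |

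These are pilot standard deviations and only indicate scale, but they show that the two weightings are not interchangeable.

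**The case against.** The strongest reply is that the planned inference does not depend on direction. Hypothesis 3 is symmetric, D.7.1.3 speaks of assessing an association, and D.7.2 powers a correlation. That stands: under common weights, neither the test nor the power changes.

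Several stronger readings are tempting, and the documents do not support them.

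- *The ecological effect will be overstated by 38%.* No section inverts the slope. The factor 1.38 arises only if someone takes that step. Because the plan expects |r| above 0.85, it is also the upper end under the plan's own assumption.
- *Adjustment for energy intake is lost.* With the same weights and covariates, the adjusted test of the AEE–obesity association is identical in both directions. Only the coefficient's scale and meaning change.
- *This slope is the only population-level effect measure.* D.7.2 also plans to compare mean AEE between the groups with the highest and lowest obesity, and D.7.1.3 compares site means. Those comparisons place AEE on the outcome side, so the written direction has some logic as description. They still do not give obesity per unit of AEE.
- *Table 1 shows the size of the discrepancy in BMI units.* It cannot. Across its ten sex-by-site pairs, AEE in kcal/d and population mean BMI correlate at +0.39, so imposing −0.85 on them would not describe those data.

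It is also fair to say that D.8 does not rest the project's success on the group comparisons. That limits the weight of the point but does not resolve the contradiction.

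**Conclusion.** The point holds as a mismatch between the specified model and the study's question. The written slope is on the wrong axis for estimating how obesity differs with AEE, and the weights belong to the wrong variable. The association test and the D.7.2 power figures are not impaired by direction alone. The size is therefore a matter of interpretation and weighting: a coefficient that cannot be compared with the person-level slopes, and group weights that could differ by a factor of about two for a single group (17.8% against 8.8%) if the pilot standard deviations and equal group sizes apply. The factor 1/r² is a caution against inverting the result, not a bias in the plan. It takes the least-squares slope of mean obesity on mean AEE as the target, ignores sampling error in the AEE means, and is only approximate once the two directions use different weights. This should be corrected before analysis, but it is not a threat to the validity of the Hypothesis 3 test.

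**What to change.** Rewrite the sentence in D.7.1.3 so that mean obesity/relative weight is the dependent variable and mean AEE the predictor, with weights equal to the inverse squared standard error of each group's mean obesity measure. Keep the usual-intake quantiles as covariates in that model. Report the slope as the difference in the obesity measure per 100 kcal/d of AEE, with its confidence interval. Name the same dependent variable in D.7.2, item 3.

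The data and software are unchanged, and the edit is about one sentence. The one downside is that the new weights may move the fitted slope and the p-value slightly from what the present weights would give, so the change should be made and dated before the group means are analysed.

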## D.7.2 Power Analysis

A statistical justification for the selected sample size is provided for each aim of the study according to the suggested analytical plan. Sample size estimation for each of these hypotheses will be obtained, and the maximum number required to test them with sufficient power (80% or higher) will be selected.

- 1) PA is negatively related to percent body fat and CV risk factors in the study populations at baseline.

It has been previously estimated (cf. Preliminary Studies) that the correlation between PA, measured with DLW, and body composition is between -0.6 and -0.5. A correlation of -0.33 or smaller (larger in absolute value) will be detectable with 83% power and maximum probability of type I error alpha = 5% using a one-sided Fisher's Z test and 75 subjects per site [194].

- 2) PA is negatively related to change in body fat composition.

- a) *Physical Activity Measured by Accelerometer:*

PA, measured by the accelerometer, is associated with changes in body composition. For design purposes we will use the approach described above in the analysis section (see D.7.1.2. method 3). That is, two AEE groups will be formed by using the median AEE as the cut point. A method developed by Frison and Pocock [195] will be applied to compare mean changes between groups in a longitudinal analysis, adjusting for baseline values. In this method the following assumptions are made: the correlation between any 2 weight determinations is ~ 0.60 and the minimum acceptable difference between the means is 0.25 standard deviations (i.e., effect size equals 0.25) [186]. There will be one baseline measure of weight and two follow-up measurements. An analysis of covariance approach will be used to adjust for baseline values. Thus, to detect the pre-specified minimum difference with 90% statistical power we will need to accrue 460 subjects per AEE group (230 in the Low and 230 in the High group). We will accrue a total of 500 individuals per site in anticipation of a conservative total attrition rate of ~ 20%.

- b) *Physical Activity Measured by Doubly Labeled Water:*

The correlation between AEE and change in body composition is anticipated to be weaker (i.e., smaller in absolute value) than that observed between AEE and body composition at baseline. Data from previous studies (cf. Section C: Preliminary Studies) suggest that the association between AEE and body composition remains constant across studies.

Although the study is not powered to test for differences in the association across sites (i.e., effect modification), we will undertake this task to ensure that large differences among the correlation coefficients do not exist. In addition, sites in which the correlation coefficient is deemed to be similar will be combined, and then comparisons of the correlations will be performed. For the sake of illustration, assume that 2 sites ( $n = 150$  individuals) are compared to other 2 sites ( $n = 150$  individuals). Thus, a two-sample, one-sided test of the correlations, assuming -0.4 versus -0.65, will yield over 91% power, whereas the power will be over 80% for comparison of -0.45 and -0.65, and between -0.35 and -0.6 the power is greater than 85%. Combining the data samples from all 5 sites and assuming constant

association will demonstrate a correlation between AEE and change in body composition of -0.15 or smaller (larger in absolute value) with over 83% power.

3) Mean levels of AEE are negatively related to mean levels of obesity/relative weight among the populations.

As previously demonstrated, sample sizes within sites will allow us to rule out correlations larger than 0.33 (absolute value), even when AEE is determined by DLW. Furthermore, we have estimated (cf. Preliminary Studies) that the within-site correlation between AEE and body composition of individual data could be as large as 0.6. We anticipate that the correlation between mean AEE levels and mean body composition will exceed 0.85. This estimate is justified in the following manner. A Fisher's Z-transformation 5%-significance test will have over 55% power to detect this correlation with 5 values corresponding to the 5 sites of the study. However, after dividing our samples by gender there will be 10 observations (2 X 5 countries), resulting in over 95% statistical power. Assuming an effective sample size of 7, to account for within-country correlations, the statistical power is 80%. Note that additional power will be gained when weighted linear regression methods are applied to estimate the correlation (slope) between AEE and body composition using meta-regression. Given the strong a prior hypothesis we can also compare mean AEE in the groups with the highest and lowest rates of obesity to test the ecological association.

In this instance, we acknowledge that we are forced to make the assumption that important relationships will be inherently strong statistically. This assumption is justified since the unit of the analysis will be the average for the entire group in each site, and therefore estimated with precision. For example, in our study of 11,000 individuals in 8 populations we demonstrated a correlation of 0.85 between mean BMI and prevalence of hypertension [123]. To enhance our ability to find these relationships, we have selected populations from across the full range of BMI (e.g., from 21-30). We are also fully aware of the possibility of "ecological confounding" in these analyses. Thus, while a strong correlation could be observed, the causal process could be entirely different from, but simply co-linear with, the AEE relationship. We will guard against this outcome by testing the individual-level relationships first, as discussed previously.

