#### **D.7.1.1 Weight and Body Composition are Related to AEE at Baseline**

##### **D.7.1.1.1 AEE, Weight and Body Composition**

Two measures of AEE will be available. At baseline, we will have 500 participants/site with data from the accelerometer, inclusive of those who have both DLW and accelerometer (total N, all sites = 2500; 6 days

of monitoring). We will have data generated by DLW for 75 participants/site (total N, all sites = 375). The structure of the analysis will be similar with both exposure measures.

We anticipate that data for all the primary outcomes will not conform entirely to a normal Gaussian distribution. Using BMI, PAL and AEE data collected in previous studies in Maywood (n = 567) and Nigeria (n = 735), we examined the probability distributions. A formal test statistic was performed that combines kurtosis and skewness [180] as implemented in STATA with p-values less than 0.001, suggesting deviations from normality. Kernel density estimates of the BMI, AEE, and PAL distributions are depicted in Figure 7. After applying the ladder of power approach suggested by Tukey [181], we found that BMI, AEE and PAL for both sites appear to deviate from normality. Although no transformation is preferred after application of the ladder of powers method, two potential transformations are suggested by this approach, namely  $\log X$  and  $X^{-1}$ . Tukey's approach followed by formal testing will be carried out once data on all subjects in the study has been collected and a decision about data transformations has been made. Despite the lack of normality exhibited and corroborated by the statistical tests performed, a visual exploration of Figure 7 suggests only slight deviations from normality, mostly due to well-known skewness of these distributions. Thus, we anticipate the statistical methods that make use of normally distributed data will be appropriate to analyze these data. Of course, the degree of appropriateness of these methods will depend on their robustness to deviations from normality. If it is necessary, appropriate transformations will be carried out before statistical tests are performed.

**Figure 7.** Distribution estimates of main analysis variables BMI, AEE, and PAL in two sites: Maywood (US) and Nigeria.

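### D.7.2 item 1 prints 83% power for a one-sided 5% test of r = -0.33 with 75 per site; that test has 89.7% power, and 83% is the two-sided value

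*Combined protocol and SAP*

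**What the plan says.** The introduction to D.7.2 sets the criterion that "the maximum number required to test them with sufficient power (80% or higher) will be selected".

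Item 1 concerns the baseline correlation between activity measured by doubly labeled water (DLW) and body composition. It expects a correlation between -0.6 and -0.5, and states that -0.33 or stronger "will be detectable with 83% power and maximum probability of type I error alpha = 5% using a one-sided" Fisher's Z test with 75 subjects per site. The sample size agrees with D.7.1.1.1: "We will have data generated by DLW for 75 participants/site (total N, all sites = 375").

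Item 2b gives two further kinds of correlation power. The first compares two pairs of sites with 150 people in each pair: "Thus, a two-sample, one-sided test of the correlations, assuming -0.4 versus -0.65, will yield over 91% power", followed by over 80% for -0.45 against -0.65 and more than 85% for -0.35 against -0.6. The second pools all five sites under a constant association, which "association will demonstrate a correlation between AEE and change in body composition of -0.15 or smaller (larger in absolute value) with over 83% power". No sidedness, significance level or sample size is given for the pooled figure.

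Item 3 refers back to item 1 ("sample sizes within sites will allow us to rule out correlations larger than 0.33 (absolute value"). For an assumed between-population correlation of 0.85 it then says that a Fisher's Z "5%-significance test will have over 55% power to detect this correlation with 5 values", that 10 sex-by-country values give over 95%, and: "Assuming an effective sample size of 7, to account for within-country correlations, the statistical power is 80"%. It does not state sidedness.

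**The concern.** Item 1 prints every input needed to check its power: effect size, significance level, sidedness, test and sample size. The result should therefore reproduce directly, and it does not. A reader cannot tell whether the planned per-site test is one-sided with about 90% power or two-sided with 83%.

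The stake is whether the plan's stated sensitivity can be relied on. The 0.33 limit is cited again at the start of item 3 as already established. The pooled figure in item 2b also reads 83% and lacks the details that would show whether it shares the same slip. With some combinations of sidedness and sample size, that pooled figure falls below the plan's own 80% criterion.

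**Working it through.** **Inputs.** Item 1: |r| = 0.33, n = 75, alpha = 5%, one-sided. Item 2b: |r| = 0.15 pooled, and 150 v 150 for the two-sample comparison. Item 3: |r| = 0.85 with n = 5, 7 and 10. DLW total 375 (D.7.1.1.1). Attrition of up to 20% by 24 months (D.1.1), used only to test alternatives. Where item 2b prints no alpha, 5% is assumed.

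**Formula, one correlation.** Power = Φ(atanh|r| × √(n − 3) − z), with z = 1.645 one-sided and 1.960 two-sided.

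**Item 1.** atanh(0.33) = 0.3428 and √72 = 8.485, so the product is 2.909.
- One-sided, as labelled: Φ(2.909 − 1.645) = Φ(1.264) = 89.7%. Printed: 83%. Difference: 6.7 points.
- Two-sided: Φ(2.909 − 1.960) = Φ(0.949) = 82.9%. This matches the printed 83%.
- One-sided with 20% loss (n = 60): Φ(0.3428 × √57 − 1.645) = 82.7%. This also rounds to 83%, but item 1 is a baseline analysis with 75 printed, so 24-month attrition does not apply.

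Simulation of the Fisher Z test at n = 75 agrees: about 90% one-sided and 83% two-sided.

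Detectable |r| at 83% power and n = 75 is tanh((z + 0.954)/√72): 0.297 one-sided and 0.331 two-sided. The printed 0.33 is thus the two-sided limit.

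Sample size for 80% power at |r| = 0.33 is 3 + ((z + 0.842)/0.3428)²: 55.6, so 56 per site one-sided; 69.8, so 70 per site two-sided. Both are below 75.

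**Pooled r = -0.15 (item 2b, printed as over 83%).** atanh(0.15) = 0.1511.

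| n | one-sided | two-sided |
|---|---|---|
| 375 | 89.8% | 83.0% |
| 300 (375 × 0.8) | 83.1% | 74.0% |

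Two cells sit at 83%, and nothing in the text chooses between them.

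**Two-sample comparison (item 2b).** Power = Φ(|atanh r₁ − atanh r₂|/√(2/147) − z), 150 per group.

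| Correlations | printed | one-sided | two-sided |
|---|---|---|---|
| -0.40 v -0.65 | over 91% | 91.5% | 85.4% |
| -0.45 v -0.65 | over 80% | 80.1% | 70.2% |
| -0.35 v -0.60 | over 85% | 87.8% | 80.2% |

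These reproduce one-sided, as labelled, with 75 per site and no attrition. With 20% loss (120 per group) the one-sided values are about 85%, 72% and 81%, which do not reproduce the printed figures.

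**Item 3, |r| = 0.85.**

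| n | printed | one-sided | two-sided |
|---|---|---|---|
| 5 | over 55% | 55.2% | 42.7% |
| 7 | 80% | 80.7% | 71.0% |
| 10 | over 95% | 95.3% | 91.4% |

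These reproduce one-sided by the formula. Among the correlation powers with a printed sample size, item 1 is the only one that disagrees with a one-sided calculation.

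**The case against.** The strongest reply is that nothing turns on this. Item 1 clears 80% under either reading, the error understates power if the label is right, and the correlations expected at baseline (-0.6 to -0.5) have power above 99% with 75 subjects. The 0.33 limit is only background in item 3, whose own figures use r = 0.85. All of this stands, and it confines the point to the correctness of a stated figure.

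A reader might go further and infer that the plan has a one-sided convention, so that 83% must be the wrong number. The documents do not support that. D.7.2 declares no general convention: one-sided is written only in item 1 itself and in the two-sample comparison. A single mislabelling would explain both 83% figures at the full DLW samples (82.9% at 75 and 83.0% at 375). The opposite inference, that the label must be wrong, is not established either. B.9 calls the test of the study hypothesis two-sided, but explains this as meaning that either the presence or the absence of an association can be interpreted, which does not fix the tail of the test.

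A reader might also infer that the pooled figure was computed at n = 300 after attrition. That value fits one-sided, and the outcome is a change over follow-up, but the text does not print it. The neighbouring two-sample figures use 75 per site without attrition.

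**Conclusion.** The point holds as a mismatch inside one sentence. With item 1's own inputs the power is 89.7%, and the printed 83% belongs to a two-sided test. The size is 6.7 percentage points of power or, at 83% power, a detectable |r| of 0.297 against the printed 0.33. Which element is wrong cannot be determined from the documents. The calculation assumes only the usual Fisher Z approximation, which simulation supports at this sample size.

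The pooled r = -0.15 figure is incompletely specified rather than shown to be wrong: it ranges from 74.0% to 89.8% over the four combinations above.

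Two stronger conclusions might be drawn and are not supported. Item 3 contains no numerical error when read one-sided, so its missing label is only a missing detail. The per-site DLW sample is not too small for item 1: the 80% criterion needs 56 (one-sided) or 70 (two-sided), and 75 are planned.

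**What to change.** Make the label and the figure in item 1 agree, in one of two ways:

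- Keep one-sided and restate the power for r = -0.33 as about 90%, or keep 83% and restate the detectable |r| as about 0.30. The limit repeated in item 3 should match.
- Change the label to two-sided and keep 83%.

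In the same edit, state the sidedness and the sample size behind the pooled r = -0.15 figure. The sponsor should supply the sample size actually used. The choice should be consistent with the adjacent two-sample figures, which take 75 per site and reproduce only one-sided, or the reason for differing should be given. Adding the sidedness to item 3 would complete the record.

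If two-sided testing is intended throughout, more must change: the two-sample figures become about 85%, 70% and 80%, and item 3 becomes about 43%, 71% and 91% for n = 5, 7 and 10 by the formula. Some of these fall below the 80% criterion, and the text should say so.

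The cost is wording in D.7.2. Recruitment and procedures do not change, and the DLW sample of 75 per site stands for item 1 under either choice.
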